8.4.1. Chemistry

The laboratory assessment will include the following tests:

total protein, albumin, sodium, potassium, total calcium, calcium corrected, blood urea nitrogen (BUN), creatinine, creatinine clearance, glucose, aspartate aminotransferase (AST), alanine aminotransferase (ALT), alkaline phosphatase, total bilirubin (total), and direct bilirubin, amylase, lipase.

8.4.2. Hematology

The laboratory assessment will include the following tests:

Hemoglobin (HGB), hematocrit, platelet count, red blood cell (RBC) count, mean corpuscular volume (MCV), mean corpuscular hemoglobin (MCH), reticulocytes (absolute), reticulocytes (%), white blood cell (WBC) count, neutrophils (absolute), lymphocytes (absolute), monocytes (absolute), eosinophils (absolute), basophils (absolute), neutrophils (%), lymphocytes (%), monocytes (%), eosinophils (%) and basophils (%).

8.4.3. Coagulation

The laboratory assessment will include the following tests:

Prothrombin time (PT), partial thromboplastin time (PTT), and international normalized ratio (INR). Both INR and PTT will be graded.

8.4.4. Urinalysis

The laboratory assessment will include the following tests:

pH, microscopic examination, specific gravity, ketones, protein, glucose, blood

8.4.5. Additional Tests

The laboratory assessments will include the following tests:

Serum: Troponin I, and troponin T. There will be a summary for local labs only.

8.4.6. Analysis of Liver Function Tests

A summary of Hepatobiliary Laboratory Abnormalities will be displayed. The general rules are:

- Categories are for subject counts and percentages, not events.
- To be counted in the denominator, the subject must have at least one post-baseline lab chemistry measurement for the specified lab tests (e.g. in the 'ALT ≥3xULN and BIL ≥2xULN' category, the denominator should include subjects who had both a post-baseline ALT value AND a post-baseline BIL value that was up to 28 days after ALT). This denominator is the most conservative for reporting percentages.
- Categories are not mutually exclusive. For example, a subject with ALT 20xULN will be included in each of the 3x, 5x, 8x, 10x, and 20x categories.
- If direct bilirubin is available, on the same day, the direct bilirubin as a portion of the total bilirubin must be ≥35% when total bilirubin is ≥2xULN. If all criteria for Hy's Law are satisfied except direct bilirubin exists and is <35% then the record will not be considered a Hy's Law event. If total bilirubin value is not provided within 28 days on or after ALT value, direct bilirubin cannot be used in place of total bilirubin in the Hy's law criteria.
- Hepatocellular injury is defined as ((ALT/ALT ULN)/ (ALP/ALP ULN)) ≥5 and ALT ≥3xULN. ALT and ALP values must occur on the same day. The denominator should include subjects who had both a post-baseline ALT and ALP on the same day. In addition, the denominator for Hepatocellular injury and BIL ≥2xULN should include subjects who had both a post-baseline ALT and ALP on the same day as well as BIL on or up to 28 days of that day.

8.5. Other Safety Measures

Unless otherwise specified, the denominator in percentage calculation at each scheduled visit will be based on the number of subjects with non-missing value at each particular visit.

8.5.1. Vital Signs

Change from baseline in vital signs will be summarized by scheduled visit using mean, median, standard deviation, minimum and maximum.

Summaries of increase in systolic blood pressure and diastolic blood pressure from the baseline with respect to the categories defined in Section 15.8.3 will be performed. These summaries will display the number and percentage of subjects with any grade increase, increase to grade 2 and increase to grade 3 at each scheduled assessment time and in the worst-case post-baseline. Subjects with missing baseline value are to be assumed to have grade 0.

Summaries of changes in heart rate and temperature from the baseline value with respect to the categories defined in Section 15.8.3 will be performed. For heart rate and temperature, both an increase and decrease in value are of clinical concern. Subjects with missing baseline value are to be assumed to have normal baseline.

The determination of the worst-case post baseline takes into account both planned and unscheduled assessments. The percentages are based on the number of subjects in the treatment group with data for the vital sign parameter at the specified planned time.

A supporting listing will also be provided.

8.5.2. Performance Status

ECOG performance status [Oken, 1982] will be summarized at baseline and each postbaseline scheduled visit. Summaries will use frequency and percentage of subjects at each planned assessment time. A summary of change from baseline by scheduled visits will be performed.

8.5.3. ECG

A summary of the number and percentage of subjects who had normal and abnormal (clinically significant and not clinically significant) ECG findings will be displayed by scheduled visits as well as for the worst-case post-baseline (including unscheduled assessments). When more than one ECG is performed during a 'Time Period' or when there are multiple values used to determine 'Worst Case Post-Baseline', the following rules will be used to determine the worst case finding based on the interpretation and the clinical significance:

- Count the subject as 'ABNORMAL' and 'CLINICALLY SIGNIFICANT', if any of the findings are 'ABNORMAL' and 'CLINICALLY SIGNIFICANT' during the time period/Post-Baseline.
- Else count the subject as 'ABNORMAL' and 'NOT CLINICALLY SIGNIFICANT', if any of the findings are 'ABNORMAL' and 'NOT CLINICALLY SIGNIFICANT' and none of the findings are 'ABNORMAL' and 'CLINICALLY SIGNIFICANT' during the time period/Post-Baseline.
- Else count the subject as 'NORMAL' if there is a finding of 'NORMAL' and none of the findings are 'ABNORMAL during the time period/Post-Baseline.
- Otherwise, do not count the subject during the time period/Post-Baseline, i.e. little n will reflect that the subject is not counted in the time period/Post-Baseline.

The QTc values based on Fridericia formula will be rounded to the integer and the values will be categorized into the ranges identified in Section 15.8.2. Summaries of grade

increase will be provided. These summaries will display the number and percentage of subjects with any grade increase, increase to grade 2 and increase to grade 3 at each scheduled assessment time and in the worst-case post-baseline (including unscheduled assessments). For grade increase summaries, missing baseline values will be assumed to be grade 0. For triplicate values, grades associated with the highest value will be reported.

The changes in QTc values will be categorized into the clinical concern ranges which are specific to changes in QTc: 31-60 and >60 msec. A summary of change in QTc value will display the number and percentage of subjects with the worst-case post-baseline (including unscheduled assessments). For numerical values measured in triplicate, averages at each visit will be used for this analysis.

Listings of all ECG values will be provided.

8.5.4. LVEF

Absolute change from baseline in LVEF will be summarized at each scheduled assessment time and in the worst-case post-baseline. Only the post-baseline assessments that used the same method (ECHO or MUGA) as the baseline assessments will be used to derive the change from baseline. The change from baseline will be categorized as identified in Section 15.8.4.

8.5.5. Liver Events

For any liver events that occur during the study, the liver event information for Roussel Uclaf Causality Assessment Method (RUCAM) score will be summarized, including whether the subject was age 55 or over, whether the subject became pregnant, liver imaging normal or not, a biopsy was taken or not, whether there was fasting or significant dietary change, whether the subject took any unconventional medications, timing when the event occurs (while on treatment or after stopping treatment) and listings will be provided for time from first dose to start of liver event and time from last dose to start of liver event.

For subjects with multiple events, the first event will be used for the summary tables. All events with subject level details will be displayed in a supporting listing.

8.5.6. DEXA Bone Densitometry

A listing of DEXA bone densitometry data from local labs will be provided for all subjects. These will include scan region and assessment, site, planned time, date, study day, BMD in g/cm2, Z-scores, T-scores, and institution assessment. A summary of bone mineral density shifts from baseline relative to normal range will also be provided.

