8.3.6. Bone Mineral Density

In order to assess the clinical bone safety of GSK3326595, dual energy x-ray absorptiometry (DEXA) scans will be performed on all patients at baseline and every 8 weeks thereafter (Section 8.1). This evaluation has been deemed most relevant as it is the clinical gold standard to detect any unexpected changes in bone mineral density (BMD), which may suggest an increased risk of fracture.

For consistency in the assessment, DEXA scans should be performed on the same machine for all evaluations on a particular subject when possible. For more details, please refer to the SRM.

Locally collected DEXA scans may be read centrally.

Post Protocol Amendment 8 implementation, bone assessments (DEXA) will be performed at the discretion of the investigator. The data will be collected via a paper process and submitted to the Sponsor only if reporting criteria is met for SAEs, AESIs, or AEs leading to treatment discontinuation. Locally collected data will not be read centrally.

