5.2. Baseline Definitions

Baseline will be defined as the most recent, non-missing value prior to or on the first study treatment dose date for GSK3326595, including those from unscheduled visits.

For laboratory data, baseline will be defined as the most recent, non-missing value from a central laboratory prior to or on the first study treatment dose date. If there are no central labs collected for a subject and lab test prior to or on the first dose of study treatment, the most recent, non-missing value from a local laboratory prior to or on the first dose of study treatment will be defined as the baseline value.

If the latest pre-dose value is collected on the day of treatment, the time of treatment will be used to identify the baseline value. If time is not collected, Day 1 assessments are assumed to be taken prior to first dose and used as baseline.

Unless otherwise stated, if baseline data are missing, no derivation will be performed and baseline will be set to missing.

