3.57	All Treated	ODMOD1	Summary of Dose Reductions of GSK3326595	ICH E3 Part 1 (by dose), Part 2 (by cohort), Part 1/Part 2 300mg/400mg/Total/Overall, Part 3 (by dose)	SAC
3.58	All Treated	ODMOD1	Summary of Dose Reductions of Pembrolizumab	Part 3	SAC
3.59	All Treated	ODMOD2	Summary of Dose Interruptions of GSK3326595	ICH E3 Part 1 (by dose), Part 2 (by cohort), Part 1/Part 2 300mg/400mg/Total/Overall, Part 3 (by dose)	SAC
3.60	All Treated	ODMOD3	Summary of Dose Delays of Pembrolizumab	Part 3	SAC
3.65	All Treated	AE1	Summary of Adverse Events Recorded as Dose-Limiting Toxicities by Preferred Term– Part 1	ICH E3 Part 1	SAC
ECOG	Performance				
3.66	All Treated	PS1A	Summary of ECOG Performance Status	ICH E3 Part 1 (by dose), Part 2 (by cohort), Part 1/Part 2 300mg/400mg/Total/Overall, Part 3 (by dose)	SAC
Ocular	Adverse Event	s			
3.70	All Treated	from IB 2022	Summary of Adverse Events (Ocular Events) by Preferred Term	Part 1, Part 2, Part 3, Part 1+2	SAC
3.72	All Treated	from IB 2022	Summary of Adverse Events (Bone- Related Events) by Preferred Term	Part 1, Part 2, Part 3, Part 1+2	SAC
Bone N	Aineral Density	Shifts			

		IDSL / Example			
No.	Population	Shell	Title	Programming Notes	Deliverable
3.75	All Treated	from IB 2022	Summary of Bone Mineral Density Shifts from Baseline Relative to Normal Range, Among Patients with Pre- Treatment Baseline DEXA Scan – Local Labs	Part 1, Part 2, Part 3, Part 1+2	SAC
3.77	All Treated	from IB 2022	Summary of Bone Mineral Density Shifts from Baseline Relative to Normal Range, Among Patients with First DEXA Scan Performed on Treatment – Local Labs	Part 1, Part 2, Part 3, Part 1+2	SAC

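### Bone density is summarised only as shifts relative to the normal range, so a fall within a category appears in no summary table; Table 3.77 should also stop calling its reference scan Baseline

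*SAP*

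**What the plan says.** Protocol 8.3.6 schedules DEXA for all patients at baseline and every 8 weeks, and gives the purpose as "to detect any unexpected changes in bone mineral density (BMD), which may suggest an increased risk of fracture".

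SAP 8.5.6 plans two outputs. The first is a listing (Listing 76) by scan region, date and study day, which includes "BMD in g/cm2, Z-scores, T-scores, and institution assessment". The second is the summary: "A summary of bone mineral density shifts from baseline relative to normal range will also be provided".

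Appendix 12 (SAP 15.12.7) turns that summary into two tables:

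- Table 3.75 is restricted to patients with a scan before dosing ("Among Patients with Pre- Treatment Baseline DEXA Scan").
- Table 3.77 is titled "Summary of Bone Mineral Density Shifts from Baseline Relative to Normal Range, Among Patients with First DEXA Scan Performed on Treatment".

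The general rule in SAP 5.2 is: "Baseline will be defined as the most recent, non-missing value prior to or on the first study treatment dose date for GSK3326595". Unless otherwise stated, "if baseline data are missing, no derivation will be performed and baseline will be set to missing".

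**The concern.** The scans are made to detect change in BMD, and BMD is recorded as a continuous measurement, but the only aggregate output counts movement between categories. A large fall inside the normal range counts as no shift, while a trivial fall across the limit counts as one.

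The SAP treats other continuous safety measures differently. Laboratory values (8.4) and vital signs (8.5.1) get change-from-baseline summaries by visit, and LVEF (8.5.4) gets absolute change by visit and worst case. No reason is given for leaving BMD out.

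Bone-related events are adverse events of special interest (Protocol 9.1.2). Change in organ-specific parameters is also among the examples of safety change in the Part 1 and Part 3 primary endpoints. At stake is how well the summary tables would show a consistent but moderate loss.

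A smaller point concerns Table 3.77. It reports a shift from Baseline in patients whose first scan came after dosing began, and who therefore have no baseline in the ordinary sense of SAP 5.2.

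**Working it through.** **What is summarised.** The DEXA entries in Appendix 12 are Listing 76 and Tables 3.75 and 3.77. None gives mean, absolute or percent change in BMD or T-score. SAP 15.8 sets no BMD categories, so the normal range is not defined. The SAP also does not say which of the 8-weekly scans enters the shift. Both tables point to a shell from the 2022 IB that is not in the documents.

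**Size.** The plan gives no figure to reproduce. All inputs here are assumptions, not taken from the documents:

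- baseline T-score ~ N(μ, 1), with μ = 0, -0.5 or -1
- normal means a T-score above -1
- true loss of 0.5 T-score units in every patient
- SD of observed change 0.3
- either a single post-baseline scan (k = 1) or the worst of four with independent variation (k = 4)

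Among patients normal at baseline,

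P(shift) = ∫ from -1 to ∞ of φ(t - μ) · {1 - [1 - Φ((-1 - t + 0.5)/0.3)]^k} dt, divided by 1 - Φ(-1 - μ).

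| Mean baseline T | Shift, one scan | No shift | Shift, worst of four | No shift |
|---|---|---|---|---|
| 0 | 19% | 81% | 32% | 68% |
| -0.5 | 28% | 72% | 45% | 55% |
| -1 | 37% | 63% | 57% | 43% |

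A hand check at μ = 0 with a fixed loss and no scatter gives (Φ(-0.5) - Φ(-1)) / (1 - Φ(-1)) = (0.3085 - 0.1587) / 0.8413 = 17.8% shifting, close to the 19%.

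**Sensitivity to the loss.** With a fixed loss, one scan and no scatter, the share of initially normal patients showing no shift is:

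| Mean baseline T | Loss 0.25 | Loss 0.5 | Loss 1.0 |
|---|---|---|---|
| 0 | 92% | 82% | 59% |
| -0.5 | 87% | 72% | 45% |
| -1 | 80% | 62% | 32% |

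**What a numeric summary would show.** Take 20 patients with the same 0.5 loss and SD 0.3. The standard error is 0.3/√20 = 0.067, and with t(19) = 2.09 the half-width is 0.14. The mean change would be -0.5, with a 95% CI of about -0.64 to -0.36, whatever the baseline.

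**Table 3.77.** SAP 5.2 places baseline on or before first dose, whereas this table's patients were first scanned on treatment. No other reference is defined for them, so the first on-treatment scan presumably serves; this is an inference, because the shell is not available. Any loss before that scan falls outside the comparison, and no analysis can restore it.

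**The case against.** Four points weigh on the other side.

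- **The report would still contain the loss.** Listing 76 gives each subject's BMD, T- and Z-scores by region and study day. Bone-related adverse events are summarised (SAP 8.3, Table 3.72). Protocol 9.1.3 requires clinically significant worsening on safety assessments to be recorded as an adverse event whether or not a range limit is crossed. A reader might infer that bone loss is hidden from the report; the documents do not support that. It is diluted in the summaries.
- **A shift table is not blind.** In the least sensitive cell of the first table, 19% of 20 patients is about 4 newly below normal, which a reader would notice. An 81% no-shift rate is the top of the range, not a typical value. Shifts relative to a range are also a defensible descriptive choice for local scans, which use the same machine only when possible. This reduces the size of the point but does not explain why BMD lacks the summary given to other measures.
- **Table 3.77 need not break SAP 5.2.** A reader might infer a breach, but the missing-baseline sentence allows exceptions stated elsewhere. The table's title discloses the on-treatment first scan, and its patients are already kept apart from Table 3.75. What stands is a loose label.
- **Exposure in Table 3.77 is unknown.** DEXA came in with Amendment 5 (April 2020), so a reader might infer that the table holds mainly the longest-exposed patients, in whom loss is most understated. The documents give neither a count nor exposure for this group, and a later patient who missed the screening scan would also fall into it.

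**Conclusion.** The point holds in limited form. The planned BMD summaries record only category shifts, so falls within a category reach no summary table. For an assumed uniform loss of 0.5 T-score units, with SD of change 0.3 and normal above -1, about 43-81% of initially normal patients would show no shift across mean baselines of 0 to -1 and one scan or the worst of four. The figure moves with the assumed loss and with the table layout, which is not available. The gap is one of sensitivity in the summaries. It does not amount to missing data or to concealment, and it does not show that the safety conclusions would be wrong. The Table 3.77 point is a matter of labelling.

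**What to change.** In SAP 8.5.6 and Appendix 12, for patients with a pre-treatment scan, add a table of absolute and percent change in BMD (g/cm2) by scan region and scheduled visit, plus worst post-baseline change, in the change-from-baseline layout already used for laboratory values. State which normal range and which post-baseline scan the shift tables use.

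In Table 3.77, replace Baseline with *first on-treatment scan* and show time on drug at that scan. Keep the table separate from Table 3.75, as already planned.

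The cost is one added table and one retitled table, from data already in Listing 76; no new collection is needed. The drawback is small numbers per region and differing local machines, so the numeric summary should be read descriptively.

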8.5.7. Ophthalmic Assessments

Listings of optical coherence tomography from local lab results with age/sex/race, date, study day, machine type, and left and right eye results in microns will be provided. In

addition, a listing of best corrected visual acuity (Snellen Acuity Equivalent) results will also be provided.

PHARMACOKINETIC ANALYSES 9.

The pharmacokinetic (PK) analyses will be based on the Pharmacokinetic Population, unless otherwise specified.

Table 12 provides an overview of the planned analyses, with full details being presented in Appendix 12: List of Data Displays.

Endpoint /	Unt	ransfo	ormed					Log-Transformed						
Parameter/ Display	Stat	S		Sum	nmar	Indi	vidu	Stat	S		Sum	ımar	Indiv	/idu
Туре	Ana	Analysis		у		al		Analysis		у		al		
	Т	F	L	Т	F	F	L	Т	F	L	Т	F	F	L
Drug Concentration														
Plasma or Urine				Y	Y	Υ	Υ							
Pharmacokinetic														
Concentration														
Pharmacokinetic Parameters														
Plasma or Urine				Υ			Y							
Pharmacokinetic														
Parameters														
Dose proportionality analysis														
Food effect study														
Relative Bio-availability study														

Table 12 **Overview of Planned Pharmacokinetic Analyses**

1. NOTES:

T = Table, F = Figure, L = Listings, Y = Display generated

Stats Analysis = Represents TFL related to any formal statistical analyses (i.e. modeling) conducted.

Summary = Represents TFL related to any summaries (i.e. descriptive statistics) of the observed raw data.

Individual = Represents FL related to any displays of individual subject observed raw data.

9.1. Drug Concentration Measures

PK analysis of GSK3326595 and pembrolizumab (apply to Part 3 subjects only) drug concentration-time data will be conducted by non-compartmental methods under the direction of GSK CPMS.

Drug concentration-time data will be listed for each subject and summarized by descriptive statistics at each time point. Summary tables/figures will use planned relative time on x-axis; while individual figures will use actual time after dose on x-axis.

9.2. Pharmacokinetic Parameters

9.2.1. **Deriving Pharmacokinetic Parameters**

• Refer to Appendix 5: Data Display Standards & Handling Conventions (Section 15.5.2 Reporting Process & Standards for Pharmacokinetic).

- The pharmacokinetic parameters will be calculated by standard non-compartmental • analysis according to current working practices [SOP 314000 and GUI 51487] and using Phoenix winnonlin.
- All calculations of non-compartmental parameters will be based on actual sampling times.
- Pharmacokinetic parameters described in Table 13 will be determined from the plasma concentration-time data, as data permits.

T	Table 13	Derived Pharmacokinetic Parameters
	_	

Parameter	Parameter Description
AUC(0-t)	Area under the concentration-time curve from time zero to the time of the last quantifiable concentration $(C(t))$ will be calculated using the linear trapezoidal rule for each incremental trapezoid and the log trapezoidal rule for each decremental
	trapezoid.
AUC(0-∞)	Area under the concentration-time curve extrapolated to infinity will be calculated
	as:
	$AUC = AUC(0-t) + C(t) / lambda_z$
AUC(0-т)	Area under the concentration-time curve from time zero to the predose of the next
	dose. For BID administration, AUC (0-12) will be computed
Cmax	Maximum observed plasma concentration, determined directly from the
	concentration-time data.
tmax	Time to reach Cmax, determined directly from the concentration-time data.
t1/2	Apparent terminal half-life will be calculated as:
	$t\frac{1}{2} = \ln 2 / \text{lambda}_z$
CL/F	Oral clearance
TI	time invariance will be calculated as:
	• $TI = \frac{AUC(0-\tau), Day 15}{15}$
	$AUC(0-\infty), Day 1$
AR	accumulation ratio will be calculated as:
	• AB = $\frac{AUC(0-\tau), Day 15}{15}$
	$AUC(0-\tau), Day 1$

1. NOTES:

Additional parameters may be included as required.

Lambda z is the terminal phase rate constant. •

GSK3326595 concentrations will be determined in urine samples to determine urinary recovery of unchanged drug and renal clearance.

Urinary Recovery: The urinary recovery of unchanged drug in a complete collection up to a fixed time point (Ae(0-x)), over a dosing interval (Ae(0- τ)), or up to the time of the last measurable urinary concentration when concentrations in subsequent collections are non-quantifiable (Ae($0-\infty$)), will be calculated as the sum of the products of concentration and urine volume over the appropriate collection intervals.

Urinary Excretion Rate: The urinary (renal) excretion rate of unchanged drug may be calculated based on urine collection over a specified time interval. In situations when

plasma drug concentrations are non-quantifiable, the estimation of elimination rate constant and elimination half-life of a drug can be made by analyzing urinary excretion rate data.

Renal Clearance: Renal clearance will be calculated from the ratio of the appropriate values for urinary recovery and area under the concentration-time curve e.g.,

$$CLr = \frac{Ae(0-x)}{AUC(0-x)}$$

